### **1. ABSTRACT:**

This is a prospective, controlled pilot study to test the effectiveness of High Flow Nasal Cannula (HFNC) therapy in infants 12 months or younger when compared to nasal O2 for treatment of Obstructive Sleep Apnea (OSA).

### **2. PURPOSE OF STUDY:**

To test the effectiveness of High Flow Nasal Cannula (HFNC) therapy in infants as a treatment for obstructive sleep apnea (OSA) and compare with current standard of care, nasal O2

### **3. BACKGROUND:**

The current standard of care at Cincinnati Children's Hospital (CCHMC) for treating OSA in infants less than 6 months of age is by a continuous flow of oxygen by nasal cannula[1]. This is generally referred to as nasal continuous positive airway pressure or NCPAP. A nasal cannula (NC) is used with oxygen at low flows (1/4 lpm up to 1 lpm ) to deliver supplemental oxygen to reduce oxygen desaturations associated with apneic episodes and to provide a positive pressure flow to maintain an open airway. At the CCHMC sleep center, the titration of the lpm flow of oxygen is done during a clinical polysomnography (PSG) with continuous monitoring of cardiorespiratory parameters per SOP 031. At Children's Mercy Hospital (CMH) the titration of lpm flow oxygen is done during the clinical polysomnography with continuous monitoring of cardiorespiratory parameters per Oxygen Administration Policy (Attachment 1).

High Flow Nasal Cannula (HFNC) therapy is a non-invasive treatment providing respiratory support. Over the last decade, HFNC has increasingly been used for oxygen delivery in neonatology departments, gradually replacing nasal continuous positive airway pressure (CPAP). Its use in pediatrics departments is more recent. HFNC is designed to administer a heated and humidified mixture of air or oxygen or a mixture of both at a flow higher than the patient's inspiratory flow. There is currently no single, simple definition of high flow. In infants, it usually refers to a flow of >2 l/min and in children it is considered >6 l/min. High flow presents several advantages over conventional 'low-flow' oxygen therapy in terms of humidification, oxygenation, gas exchange, and breathing pattern[2].

Advantages of HFNC include providing a relative humidity of nearly 100% with the gas warmed to between 34°C and 37°C. Some research has shown this to improve mucociliary clearance. Another benefit of humidification is improved inspiratory flow by reducing resistance in the nasal mucosa induced by dry and cold gas. These resistances are thought to make up nearly 50% of the total resistance of the respiratory system. Several studies have shown that a flow higher than the patient's inspiratory flow provides better oxygen delivery than low-flow oxygen therapy or high-concentration oxygenation mask. This observation has been explained as the effect of a high flow on the oropharyngeal dead space, washing out oxygen depleted gas and reducing CO2 rebreathing. The extrathoracic dead space is proportionally two to three times greater in children than in adults. It may measure up to 3 mL/kg in newborns and becomes similar to the

adult volume only after 6 years of age (0.8 mL/kg). Consequently, the younger a child is, the greater the effect of a high flow on oxygenation and CO2 clearance[3].

Studies contrasting the delivered flow to the generated pressure as measured by pharyngeal pressure are limited and the results showed wide variations in inter- and intra-subject variability. The pressure is determined not only by the flow, but also by the ratio of the prong/nostril fit and whether or not the mouth is closed. One study of infants with viral bronchiolitis suggested that a flow  $\geq$  7 l/min created positive pharyngeal pressures similar to CPAP. The positive pressures generated by the device prevent pharyngeal collapse, which may be very pronounced in OSA, and HFNC can thereby support the inspiratory effort of patients[3].

Three rare incidents of pneumothorax or pneumomediastinum with use of HFNC have been reported with the cause believed to be from increases in end expiratory lung volume. These incidents occurred on a 2-month old (bronchiolitis), a 22 month- old (post trauma and mechanical ventilation), and a 16 year old (post-anesthesia). Flow rates ranged from 6–20 L/min at the time of the complication. They all had significant hyperinflation at the time of the development of air leak. The risk of generating excessive pulmonary pressures in children with OSA is reduced because the patients are asleep; with shallower tidal breathing and heated humidified air to prevent bronchospasm. This risk will be further minimized in this study since all subjects will be directly monitored for respiratory flow, effort, and gas exchange throughout the intervention [4, 5].

#### **4. STUDY DESIGN:**

This is an interventional prospective controlled pilot study to compare to standard of care the effectiveness of HFNC therapy in infants aged 12 months and younger to treat OSA.

The study intervention will occur for approximately 3 to 4 hours immediately prior to a scheduled clinical polysomnography (PSG). Subjects will be prepared for standard clinical PSG and after asleep, the intervention will be titration of room air at different pressure flows delivered by OptiFlow HFNC system. At the end of the research portion of the PSG, the clinical PSG will begin with the standard of care treatment, the nasal O2 titration for OSA. The results of the clinical PSG will serve as control comparison for the research intervention.

#### **5. DURATION:**

For outpatients, the duration of the study for subjects will be about 1 month and involve 2 visits that will be incorporated into a clinical visit and a clinical PSG (polysomnography). For inpatients, the duration of the study for the subject will be 1 night with a clinical PSG (polysomnography).

The duration of the study will be about 12 months with an additional 12 months for analysis.

#### **6. SELECTION & RECRUITMENT OF PARTICIPANTS:**

##### **A. Number of participants**

We will recruit about 10 subjects.

##### **B. Inclusion/Exclusion criteria**

###### **Inclusion**

- Infants  $\leq$  12 months
- Diagnosis of OSA from previous PSG

**Exclusion**

- Infants who on previous PSG had central apneas > 50% of the AHI (apnea hypopnea index)

#### **D. Recruitment**

At Cincinnati Children's Hospital, participants will be recruited from the Pulmonary / Sleep Disorders Clinic and the inpatient pulmonary consults, including the Newborn Intensive Care Unit (NICU). Potential study participants will be identified by study physicians who will notify and request a member of the research team to discuss participation with the family about the research study. Eligibility based in inclusion exclusion criteria will be reviewed before contacting potential study participants. Eligible candidates who are interested, willing and give parental permission for their infant to participate will be enrolled. Any recruitment materials used will be submitted to the IRB for approval prior to use.

At Children's Mercy Hospital, participants will be recruited from the Pulmonary and Sleep Disorders Program and the inpatient pulmonary consults, including the Newborn Intensive Care Unit.

#### **E. Vulnerable Populations**

Additional efforts will be made to protect this vulnerable population. Parents will be given clear explanations to define the research portion of the scheduled PSG from the clinical portion as the two will be scheduled on the same day. Parents will be given time to have their questions answered and will be informed that they can withdraw their infant at any point in the study.

### **7. PROCESS OF OBTAINING CONSENT:**

We are asking for a waiver of written HIPAA authorization to identify potential subjects by review of medical records for inclusion/exclusion criteria on the inpatient pulmonary consult team and pending clinic visits. Signed HIPAA authorization will be obtained at the time of written informed consent.

The parent will be given the consent for the study and it will be reviewed with the parent by a member of the research team and time given for questions. The parent will sign the consent after all questions are answered and a signed copy of the consent form will be given to the parent to keep. The parent will be informed that this research is voluntary and that they are able to withdraw their infant at any time. No study related procedures will be done prior to consent being signed.

#### **For non-English speaking subjects:**

At CCHMC, non-English speaking participants will be consented using a short form consent process as per CCHMC SOP 41-1.8. The approved long consent form will serve as the summary of the research. At CMH, non-English speaking participants will be consented using a short form consent process as per CMH guidelines.

## 8. STUDY PROCEDURES:

Visits:	Screen visit	PSG Visit
Sign consent	X	
Med record review	X	X
H&P	X	X
Length, weight	X	
3 hr PSG with HFNC titration procedure		X
Capillary blood gas (not done at CMH)		X

**Screening visit:**

The screening visit will be during a scheduled clinic visit or chart review once patient is identified with the help of the inpatient pulmonary consult team. Medical record review will include review of Inclusion/exclusion criteria from previous PSG, medical history and recent H&P including length and weight. Informed consent will be obtained

**PSG Visit:**

Approximately 3 to 4 hours prior to a scheduled clinical polysomnography (PSG), subjects will be prepared for the research portion of the PSG. The following parameters will be recorded:

- Electroencephalogram; right and left electro-oculogram; submental, tibial and intercostal electromyogram
- Electrocardiography (ECG)
- Nasal/oral airflow and through nasal pressure and thermal sensors; transcutaneous CO2 (TCO2); oxygen saturation by pulse oximeter; oximeter pulse waveform
- Snore sensor
- Video monitoring using an infrared video camera and recorded on a videotape
- Rib cage and abdominal volume changes will be recorded with a computer-assisted respiratory inductance plethysmograph

**HFNC Titration procedure**

After asleep, the titration procedure will occur in a step like manner with room air delivered by OptiFlow HFNC system. Subjects will be continuously monitored by sleep technicians who are certified respiratory therapists.

Titration will begin with flow of room air at 6 l/min for 30 minutes after returning to sleep. The subject will be observed for apnea-hypopneas, arousals and changes in O2, CO2, and flow.

If the patient continues to have obstructive respiratory events and the flow is tolerated based on pre-established criteria listed in the study SOP, then titration will continue.

Room air will be increased by increments of 2 l/min for 30 minutes to a maximum flow of 15 l/min after returning to sleep until the obstructive events have resolved or until not tolerated.

If a subject does not tolerate a titration, they will be dropped and maintained at the last tolerated flow for the remainder of the 3 hour PSG period (from start of 6 l/min titration) or a minimum of 30 minutes after returning to sleep, whichever is longest.

After the completion of the research portion of the PSG, a capillary blood gas will be drawn and the clinical PSG will begin with standard of care O2 nasal cannula titration. Blood gas will not be drawn at after completion of the research portion at CMH because it is not standard of care and it is not available.

**Airvo 2 Humidifier System and OptiFlow Junior Nasal Cannula:**

The Airvo 2 (Fisher and Paykel Healthcare, LTD, New Zealand) is a non-invasive ventilation system that delivers high flow warmed and humidified air. It is FDA cleared (510K131895).

The OptiFlow Junior nasal cannula (Fisher and Paykel Healthcare, LTD, New Zealand) has been determined by the FDA to be 510 K exempt under:

**Device Cannula, Nasal, Oxygen**

**Regulation Description** Nasal oxygen cannula.

**Regulation Number** 868.5340

**Classification** Class I (general controls). The device is exempt from the premarket notification

## **9. DATA ANALYSIS/METHODS:**

A descriptive analysis will be used for demographic data. The comparison of respiratory and sleep parameters between oxygen therapy and HFNC therapy will be done by means, standard deviation and paired two-tailed T test.

### **Future use**

At the close of the study, the data will be anonymized and the code retained in a secure location separate from the data. The data may be used by the PI for future research particularly longitudinal and safety studies.

## **10. FACILITIES and PERFORMANCE SITES:**

This study will be conducted in the CCHMC Sleep Disorders Clinic, CCHMC inpatient units including NICU and in the CCHMC Sleep Center, and CMH Pulmonary and Sleep Disorders Clinic and CMH Sleep Center (including portable bedside polysomnogram studies performed in the hospital)

## **11. POTENTIAL BENEFITS:**

This study does not offer direct benefit but offers the potential future benefit of a new treatment to this very young population that may be safer, more comfortable and effective than the current standard of care.

## **12. POTENTIAL RISKS, DISCOMFORTS, INCONVENIENCES AND PRECAUTIONS:**

- Noise: the noise level reaches about 80 dB. The decibel level is correlated with the flow and may be higher than that generated by other CPAP systems[3]. According to the CDC, 80 dB is within the safety margin that should not affect hearing [6].
- Nasal trauma: Nasal cannulas may cause irritation and pressure to the ostium, columella and septum [7]. We will evaluate nasal trauma according to the classification proposed by Buettikeral et al [8]. as mild, moderate, and severe as follows:
  - mild injury will be defined as a reddening around the nasal ostium;
  - moderate injury will be defined as bleeding either at the septum or nasal ostium;
  - severe injury will be defined as necrosis either on the septum or nasal ostium.
- Pulmonary air leaks: three episodes of pneumothorax and pneumodiastinum were reported during HFNC use [4]. At both study sites, subjects will be monitored during use of the HFNC by sleep technicians with the PSG monitoring equipment. Sleep technicians are certified respiratory therapists.

## **13. RISK/BENEFIT ANALYSIS:**

This study is minimal risk with the potential of future benefit.

## **14. DATA SAFETY & MONITORING:**

Adverse events will be defined as any illness or injury from the time of enrollment until the last study visit. Reportable events will be defined as any adverse event that is unexpected **and** related to this study **or** an accidental release of PHI. Reportable events will be reported promptly to the IRB per hospital policy. Adverse events that do not meet the criteria of unexpected **and** related as determined by the PI will be submitted in table form at the next continuing review.

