#### Adverse Events Defined

##### 1. Unexpected versus Expected Adverse Events

An *unexpected* adverse event is one that has not been listed previously in the risk section.

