##### 2. Relatedness (Attributions)

Attribution	Description
Unrelated	The event is unrelated.
Unlikely	The event is unlikely related.
Possibly Related	The event or severity of event is not usually associated, but there is no strong evidence to link the event.
Probably Related	The event or severity of event is such that it can likely be correlated.
Definitely Related	There is a strong correlation.

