##### 3. Severity Descriptors

Severity	Numerical Value	Description
Mild	1	Aware of sign, symptom, or event, but easily tolerated; does not interfere with daily routine
Moderate	2	Discomfort enough to interfere with daily routine and may require some therapeutic intervention
Severe	3	Incapacitating, significantly affects clinical status; requires therapeutic intervention
Life Threatening	4	Life-threatening; immediate intervention required
Death	5	Adverse event causes death.

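### A related severe or life-threatening air leak or nasal necrosis is, by the protocol's stated minimum, reported to the IRB only in the next continuing-review table, because both harms are listed risks

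*Combined protocol and SAP*

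**What the plan says.** Section 14 (Data Safety & Monitoring) sets two routes to the IRB. An adverse event that is both unexpected and related, or an accidental release of PHI, is a reportable event, and "Reportable events will be reported promptly to the IRB per hospital policy". Adverse events that are not both unexpected and "related as determined by the PI will be submitted in table form at the next continuing review".

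The first definition under Adverse Events Defined settles what unexpected means: such an "adverse event is one that has not been listed previously in the risk section". Nothing else enters that test.

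The risk section, section 12, includes this entry: "Pulmonary air leaks: three episodes of pneumothorax and pneumodiastinum were reported during HFNC use". It also grades nasal trauma as mild, moderate or severe, where "severe injury will be defined as necrosis either on the septum or nasal ostium".

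Section 14 then gives a five-level relatedness table and a five-level severity scale. Grade 3 is "Incapacitating, significantly affects clinical status; requires therapeutic intervention", grade 4 is "Life-threatening; immediate intervention required", and grade 5 is death. No grade is tied to a reporting time.

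**The concern.** An event is sorted by whether it was foreseen, not by how serious it is. Air leak and nasal necrosis are the gravest harms that section 12 names, and being named there takes them out of prompt reporting. A mild related event that nobody foresaw must be reported promptly. A life-threatening pneumothorax judged definitely related need not be.

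This matters because section 14 names no recipient of adverse event reports other than the IRB, and the document mentions no monitoring board. Section 13 classes the study as minimal risk, and a related grade 3 or 4 air leak would bear directly on that judgement. Recruitment is at two hospitals and includes newborn intensive care units. If such an event occurred, the protocol alone would not require the IRB to hear of it before its next scheduled review, while further infants could be enrolled.

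**Working it through.** The plan gives no figure to reproduce, so the check is to follow the rule through the text.

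**Inputs.** Section 14: the reporting rule, the definition of unexpected, the relatedness table and the severity scale. Section 12: the listed risks.

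**Step 1: the route for each combination.**

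| Listed in section 12? | Related? | Route under section 14 |
|---|---|---|
| No | Yes | Prompt report |
| No | No | Continuing-review table |
| Yes | Yes | Continuing-review table |
| Yes | No | Continuing-review table |

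**Step 2: place the two harms.** Air leak and nasal necrosis are both listed in section 12, so both are expected. Only the last two rows apply to them, and both end in the table. For these harms the relatedness judgement does not change the route.

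**Step 3: vary the severity.** Neither the reporting rule nor the definition of unexpected refers to a grade. Moving a related air leak from grade 1 to grade 3 or 4 leaves it in the third row.

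**Step 4: look for another way in for severity.** The relatedness table mentions it; for probably related, "The event or severity of event is such that it can likely be correlated". That can affect whether an event is called related. By step 2, this does not change the route of a listed event.

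**Step 5: grade 5.** Two readings are possible. The test asks whether the event is listed, and air leak is, so a fatal air leak goes to the table. Alternatively, death is itself an event that section 12 does not list, so a fatal case is unexpected and, if related, promptly reportable. The text does not decide between them. Grades 3 and 4 describe how severe the listed event is and do not name a separate outcome of this kind, so the same argument does not readily extend to them.

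**Step 6: what related means.** The table has five levels (unrelated, unlikely, possibly, probably, definitely). The reporting rule uses a yes/no criterion, and the documents do not say where the cut falls. Possibly related could go either way.

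**Step 7: apply a trigger at grade 3 or higher for related events.** Related listed events of grades 3 and 4 move to prompt reporting. Grade 5 becomes prompt on either reading in step 5. Grades 1 and 2 stay in the table. Necrosis is severe on the nasal scale in section 12, but that is a separate scale. Localised necrosis might be graded 2 in section 14, where moderate events may need some treatment, and would then remain in the table.

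**The case against.** The strongest reply is that hospital policy may already require faster notice of serious expected events. The protocol relies on outside documents elsewhere, for example the study SOP for tolerance criteria and site rules for consent. This is possible, and it limits the point to what the protocol itself requires. It does not remove the point, because section 14 attaches hospital policy only to events already classed as reportable, and listed events are not.

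A second reply is that the harm is unlikely. Section 3 calls the reported air leaks rare, says all three patients had significant hyperinflation, and argues that the risk is reduced in sleeping children with OSA. Exposure is one session of about 3 to 4 hours in about 10 infants, continuously monitored by certified respiratory therapists. All of that stands. The case rests on seriousness, not likelihood, and bedside monitoring does not set when the IRB is told.

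A third reply is that this is a design choice and not a contradiction. Severity grades can serve description alone, and no requirement in the documents is breached. That also stands, and it is why the point is rated as an improvement and not an error.

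A reader might infer that the protocol sends a related listed event of every grade, including death, to the table. The documents do not support that as a certainty, because grade 5 is open to two readings. Nor do they support the inference that early notice is forbidden: the text sets a minimum, and the investigator may report sooner.

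**Conclusion.** The point holds for related air leaks and nasal necrosis of grades 3 and 4. By the protocol's stated minimum, these go to the continuing-review table alongside mild listed events. At grade 5 the text is ambiguous.

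This is a property of the written rule. It assumes that listed means named in section 12 regardless of severity, which is what the definition says, and it makes no claim about what either hospital's policy requires. A reader might want a delay in weeks or a number of infants affected. The documents give neither the review interval nor an event rate in this population, so no such figure can be supported. The intervention, the data and the analysis are unaffected. The rating is cheap improvement.

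**What to change.** Add one sentence to the reporting rule in section 14: *Any adverse event judged related to the study and graded 3 or higher on the severity scale is promptly reportable to the IRB, whether or not it is listed in the risk section.* The existing table sentence can stay for events that do not meet this trigger, provided it is worded so that the two do not conflict.

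Also state which attributions count as related for reporting, for example possibly, probably or definitely related. Without this, both the present rule and the new trigger depend on an undefined cut.

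The trigger covers necrosis only when it is graded 3 or higher in section 14. If the sponsor wants every case covered, name the severe nasal grade of section 12 as an additional reporting trigger. The grade 3 threshold is a suggestion built on the protocol's own scale; the documents do not prescribe it.

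The cost is a short text change and possibly a few extra prompt reports in about 10 infants. If hospital policy already requires such reports, the change only brings the protocol into line with it.

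### Section 14 requires no more than a table entry at the next continuing review for a serious HFNC-related harm that section 12 lists (air leak, nasal necrosis), whatever its severity

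*Combined protocol and SAP*

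**What the plan says.** Section 14 (Data Safety & Monitoring) sets two routes to the IRB. An adverse event that is both unexpected and related goes promptly, under hospital policy, as does an accidental release of protected health information. An adverse event that does not combine *unexpected* with being "related as determined by the PI will be submitted in table form at the next continuing review" falls to that table.

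The subsection on unexpected versus expected events gives the only test: an unexpected "adverse event is one that has not been listed previously in the risk section".

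Section 12, the risk section, lists three things: noise, nasal trauma and pulmonary air leaks. Nasal trauma has three levels, and for the highest, "severe injury will be defined as necrosis either on the septum or nasal ostium". The air-leak entry cites three published episodes during HFNC.

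Section 14 also has a severity table (grades 1 to 5, from mild to death) and a five-level attribution table. Neither is tied to a reporting route or to a decision about continuing.

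**The concern.** The rule treats a foreseen harm as one that needs no prompt attention. Listing a risk in section 12 takes it out of prompt reporting, however severe the event turns out to be. A grade 1 unlisted event judged related must go promptly to the IRB, while a related pneumothorax need only wait for the table.

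The listed harms are relevant here. Section 3 puts the three published air leaks at flows of 6 to 20 L/min, one of them in a 2-month-old. Section 8 titrates from 6 l/min up to at most 15 l/min in infants of 12 months or younger. Section 11 says the study offers no direct benefit, and section 13 states that "This study is minimal risk with the potential of future benefit". A related air leak would call that rating into question. As written, further infants at either site could start HFNC before the protocol obliges anyone to reconsider it.

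**Working it through.** The plan states no event rate, so there is no figure to reproduce. The point rests on the text, and the arithmetic only shows its size.

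**The text, step by step**

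1. Prompt report: requires unexpected *and* related (section 14).
2. Unexpected: not listed in section 12; no test of severity or frequency (section 14, first definition).
3. Air leak and nasal necrosis: both listed in section 12, so neither is unexpected.
4. By 1 to 3, neither has to be reported promptly, even if definitely related. The table is the only required route.
5. Other safeguards: PSG monitoring by technicians who are certified respiratory therapists (sections 8 and 12), and flow-tolerance criteria in the study SOP (section 8). Both act on the infant wearing the cannula. No section requires notice to the other site or a decision before the next infant.

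**Size**

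Inputs: n = 10 infants (section 6) and recruitment over about 12 months, taken as 52 weeks (section 5). The per-infant chance p of a listed serious harm is not given. I assume 0.1% to 1%, a range that fits the word rare in section 3.

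- Chance of at least one event, 1 − (1 − p)^10: 0.0100 at p = 0.001; 0.0956 at p = 0.01.
- Expected number of infants treated after a first event, averaged over all outcomes, 10 − [1 − (1 − p)^10]/p: 0.045 and 0.44.
- Expected further harms among them at constant p: 0.045 × 0.001 = 0.000045, and 0.44 × 0.01 = 0.0044.

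If an event does occur, how many infants follow before the table is due? Assume even enrolment over 52 weeks and a continuing review every L weeks (the interval is not stated). The mean wait is L/2. Of the other 9 infants, 9 × (L/52) × 1/2 are treated in that time:

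| Assumed interval | Mean wait | Further infants treated |
|---|---|---|
| 13 weeks | 6.5 weeks | 1.1 |
| 26 weeks | 13 weeks | 2.3 |
| 52 weeks | 26 weeks | 4.5 |

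These are exposures, not harms.

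**The case against.** The strongest case against is that the harm is unlikely and the exposure short. Section 3 says that "Three rare incidents of pneumothorax or pneumomediastinum with use of HFNC have been reported", notes significant hyperinflation in all three patients, and argues that the risk is reduced in sleeping children with OSA. Exposure is one session of about 3 to 4 hours under continuous observation. The expected number of further harms is tiny. All of this stands, and it sets the severity.

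Four stronger readings are tempting, and the documents do not support them.

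- *That section 14 confines a listed harm to the table.* It does not. The table is a minimum duty, and nothing forbids earlier reporting or a voluntary pause.
- *That no rule anywhere would require action.* Hospital policy and the study SOP were not available and may add duties. As cited, though, the policy governs events already classed as reportable and the SOP governs flow tolerance, so neither cures the protocol text.
- *That a life-threatening or fatal air leak is clearly excluded from prompt reporting.* An investigator could argue that such an outcome is not itself listed in section 12. The definition has no severity test to settle this, so the text is at best ambiguous at the extreme.
- *That a confidence interval after a first event makes the case.* Ten infants could never show a risk as low as 0.1%: even 0 of 10 leaves a one-sided 95% upper bound of 1 − 0.05^(1/10) = 25.9%. The interval adds nothing, and I do not rely on it.

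One further limit stands. Adverse events are defined as "any illness or injury from the time of enrollment until the last study visit", and an inpatient is in the study for one night. Necrosis or an air leak first seen afterwards may fall outside the definition, and the change below does not alter that window.

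**Conclusion.** The concern holds for the protocol text. A serious HFNC-related air leak or nasal necrosis has no required route other than the continuing-review table, while a minor unlisted related event must be reported promptly. This is a stated rule with a perverse result rather than a missing detail.

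The severity is low. At an assumed per-infant risk of 0.1% to 1%, the chance of any listed serious event in 10 infants is 1.0% to 9.6%, with about 0.00004 to 0.004 further harms expected at constant risk. The case for change is that, once an event has happened, roughly one to five more infants could be treated before the table is due. That count depends on the assumed review interval and on even enrolment. The reading of sections 12 and 14 depends on none of these assumptions.

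**What to change.** Amend section 14 with one paragraph in two steps.

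1. *Reporting.* Any pneumothorax, pneumomediastinum, severe nasal injury (necrosis) or other adverse event of grade 3 or higher that is judged possibly, probably or definitely related to HFNC is reported promptly to the IRB and notified to both sites, whether or not section 12 lists it.
2. *Decision.* After a related air leak, related nasal necrosis, or a grade 4 or 5 event judged probably or definitely related, the PI records a decision to continue, modify or stop before the next infant starts HFNC.

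For other grade 4 or 5 events the second step needs at least a probable link, because the plan defines possibly related loosely: "The event or severity of event is not usually associated, but there is no strong evidence to link the event". Without that limit, background illness in NICU infants could trigger it too easily.

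The cost is a little extra reporting and perhaps a short enrolment delay. No new committee or fixed hold is needed, and the decision can be made the same day. At one infant per 52/10 = 5.2 weeks (even enrolment assumed), a decision that took 2 weeks would postpone about 2/5.2 = 0.4 infants. The 1.0% to 9.6% above is not the chance of such a delay, because the second step also covers grade 4 or 5 events beyond the listed harms.
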